9.5.2.4 Laboratory data

All laboratory data will be listed with abnormal values flagged. The laboratory values and the change from baseline for continuous laboratory parameters will be summarized at each visit. A frequency table of results for categorical laboratory parameters will be produced for the whole study duration.

Shift tables relative to the normal reference ranges will be used to summarize the change from baseline to post-baseline for each laboratory parameter. For each laboratory parameter, the patients will be classified into one of the four mutually exclusive groups (low, normal, high, and low + high).

For selected laboratory parameters, the number and percentage of patients with newly occurring or worsening laboratory abnormalities meeting the clinically notable criteria will be summarized by laboratory parameter at any time-point over the treatment period, considering all post-baseline data from scheduled, unscheduled and premature discontinuation visits. Patients with any newly occurring or worsening value meeting the clinically notable criteria will be counted under the applicable criteria.

9.7 Interim analyses

Not applicable.

9.8 Sample size calculation

The primary objective is to demonstrate that QAW039 150 mg is superior to placebo in pre-dose FEV1 following 12 weeks of post-baseline treatment. A difference of 112 mL in pre-dose FEV1 during treatment was assumed, which is similar to the model-averaged effect seen in study QAW039A2206. The standard deviation (SD) of 380 mL and between-visit correlation for pre-dose FEV1 was based on study QAW039A2206 in a similar population. A treatment discontinuation rate of 15% was assumed based on QAW039A2206 and it was assumed that half of the patients discontinuing study treatment would have week 12 FEV1

values. Simulations were used to determine the sample size due to the complex jump-to-reference missing data imputation approach for the primary analysis.

Under the outlined assumptions, a sample size of 650 patients (325 per arm) will be needed to have 90% power to observe a statistically significant difference between QAW039 and placebo at the two-sided 5% significance level in the primary analysis as shown in [Table 9-1](#). The table also shows the sensitivity of the power to deviations from the assumptions.

Table 9-1 Result of power simulations for the primary variable

Treatment effect (mL)	Discontinuation rate	Sample size	Power
112	15%	650	90.3
112	20%	650	85.9
100	15%	650	80.9

Based on 10,000 simulated trials per scenario and 250 multiple imputations for each trial. Simulations were conducted using SAS/STAT® 13.1 software, Version 9.4 of the SAS System for Linux.

9.8.1 Power for the secondary objectives

If statistical significance is achieved in the primary test, the tests for the secondary variables will be performed. The local significance level for each secondary null hypothesis will be determined based on the closed testing procedure shown in [Figure 9-1](#).

As differences in FEV1 to placebo for QAW039 150 mg once daily and montelukast 10 mg once daily appeared to be of similar magnitudes in study QAW039A2206, the power calculations for the two secondary objectives (change from baseline in daytime asthma symptoms and change from baseline in total daily SABA use) are based on the assumptions from the results of two studies comparing montelukast 10 mg once daily with placebo ([Reiss et al 1998](#), [Malmstrom et al 1999](#)). These studies suggest an averaged difference of 0.26 for change from baseline in daytime asthma symptoms between montelukast and placebo after 12 weeks of treatment and a SD of 0.94. The two studies also suggest an averaged difference of -1.34 point difference in the change from baseline in the number of daily SABA puffs between montelukast and placebo with a standard deviation of 3.82. We assume a clinically important true improvement of at least 0.5 in AQLQ+12 after 12 weeks treatment for patients that remain on treatment and a standard deviation (SD) of 1. As shown in [Table 9-2](#) all secondary endpoints have an adequate conditional power once the primary null hypothesis has been rejected, but will each have an even higher conditional power once the null hypotheses relating to the other secondary variables have been rejected.

Table 9-2 Power simulations for secondary variables

	Daytime asthma symptoms	Total daily rescue medication use	AQLQ+12
Difference of effect (δ)	-0.26	--1.34 number of puffs	0.5
SD (σ)	0.94	3.82 number of puffs	1
Local two-sided significance level once primary null hypothesis is rejected	0.0245	0.0245	0.001
Power	74%	97%	98%
Local two-sided significance level once primary and the other two secondary hypotheses are rejected	0.05	0.05	0.05
Power	83%	98%	> 99%

Power statements are based on 10,000 simulated trials per scenario and 250 multiple imputations using a jump-to-reference approach for each simulated trial. Simulations were conducted using SAS/STAT® 13.1 software, Version 9.4 of the SAS System for Linux. We assumed a treatment discontinuation rate of 15% with half of the patients discontinuing from study treatment completing the trial. The correlation structure was assumed to be the same as for the primary endpoint. Abbreviation: AQLQ+12 (asthma quality of life questionnaire for 12 years and older).

10 Ethical considerations

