9.4.2 Statistical model, hypothesis, and method of analysis

The primary objective of the study is to evaluate superiority of QAW039 150 mg once daily over placebo (with SoC asthma therapy as the background therapy) by testing the following null hypothesis (H_0) versus the alternative hypothesis (H_a):

[figure not shown]
H_0 : There is no difference in the change from baseline in pre-dose FEV1 at week 12 post-baseline for the patients treated with QAW039 150 mg once daily compared with placebo.

H_a : There is a difference in the change from baseline in pre-dose FEV1 at week 12 post-baseline for the patients treated with QAW039 150 mg once daily compared with placebo.

Familywise type I error rate control

The familywise type I error rate will be controlled at the two-sided 5% level across the primary and secondary null hypotheses using the closed testing procedure shown in [Figure 9-1](#) using the graphical method of [Bretz et al 2009](#). In this closed testing procedure, the primary null hypothesis about pre-dose FEV1 acts as a gatekeeper for the secondary null hypotheses.

Figure 9-1 Closed testing procedure for primary and secondary objectives

Vertices with associated weights denote the individual null hypotheses and their local significance levels. Directed edges between the vertices specify how the local significance levels are propagated in case of significant results. ϵ is set to a very small number in practice. Abbreviations: FEV1 (forced expiratory volume in 1 second); AQLQ+12 (asthma quality of life questionnaire for 12 years and older).

Initially, the alpha is assigned to the primary null hypothesis. Once the primary null hypothesis has been rejected, then 98% of the alpha will be distributed equally amongst the secondary null hypotheses of daytime asthma symptoms and total daily SABA use, respectively, and 2% of the alpha will be assigned to the null hypothesis for AQLQ+12. If one of the secondary null hypotheses is rejected, its local significance level will be propagated to the other secondary null hypotheses as illustrated in Figure 9-1.

Statistical model for primary variable

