9.5.1.1 Daytime asthma symptoms in patients

Daytime asthma symptoms are evaluated through four questions and each of them will be rated on a scale of 0 to 6. Higher scores indicate more severe asthma-related symptoms. A mean score will be calculated for the responses to 4 questions. The main analysis of the secondary endpoint of daytime symptoms will be performed for all patients over the entire age range (12 years and older). The baseline of daytime asthma symptoms will be defined as the average of the mean daytime asthma symptom score during the placebo run-in period. The mean of change from baseline in the daytime symptom scores over the 12 weeks of treatment will be analyzed using an analysis of covariance (ANCOVA) model in a similar fashion as the primary efficacy variable. The null hypothesis is that the treatment difference compared to placebo over the 12 weeks of treatment = 0, while the alternative hypothesis is that the treatment difference to placebo over the 12 weeks of treatment \neq 0. This model will be fitted to each of multiple imputations generated using a jump-to-reference approach as for the primary analysis.

The asthma diary included in this study to measure daytime asthma symptoms was validated in studies of patients aged 18 to 65 years ([Santanello et al 1997](#)). It was subsequently included as a measure in placebo-controlled studies of montelukast in patients aged 15 years and older ([Reiss et al. 1998](#) and [Malmstrom et al. 1999](#)) and shown to be responsive to both montelukast and inhaled beclomethasone therapy in this age range. Given the performance characteristics, particularly the responsiveness to asthma therapies, of the asthma diary are known for patients aged 15 years and older, a supportive analysis of the secondary endpoint of daytime symptoms will be included and be limited to patients aged 15 years and older.

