9.5.1.2 Total daily use of SABA

Total daily use of SABA (the number of puffs taken in the previous 24 hours) by the patient will be analyzed using ePEF/ eDiary data. The baseline of SABA use will be defined as the average of total daily SABA use during the placebo run-in period. The mean of change from baseline in the total daily use of SABA over the 12 weeks of treatment will be analyzed using an ANCOVA model in a similar fashion as the primary efficacy variable. The null hypothesis is that the treatment difference compared to placebo over the 12 weeks of treatment = 0, while the alternative hypothesis is that the treatment difference to placebo over the 12 weeks of treatment \neq 0. This model will be fitted to each of multiple imputations generated using a jump-to-reference approach as for the primary analysis.

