**Table 3-2 Power simulations for secondary variables**

	Daytime asthma symptoms	Total daily rescue medication use	AQLQ+12
Difference of effect ( $\delta$ )	-0.26	-1.34 number of puffs	0.5
SD ( $\sigma$ )	0.94	3.82 number of puffs	1
Local two-sided significance level once primary null hypothesis is rejected	0.0245	0.0245	0.001
Power	74%	97%	98%
Local two-sided significance level once primary and the other two secondary hypotheses are rejected	0.05	0.05	0.05
Power	83%	98%	> 99%

Power statements are based on 10,000 simulated trials per scenario and 250 multiple imputations using a jump-to-reference approach for each simulated trial. Simulations were conducted using SAS/STAT® 13.1 software, Version 9.4 of the SAS System for Linux. We assumed a treatment discontinuation rate of 15% with half of the patients discontinuing from study treatment completing the trial. The correlation structure was assumed the same as for the primary endpoint. Abbreviation: AQLQ+12 (asthma quality of life questionnaire for 12 years and older).

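### Protocol Table 9-2 and SAP Table 3-2: the printed powers for daytime symptoms and for SABA use cannot both follow from the one stated set of assumptions

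*Protocol*

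**What the plan says.** Protocol section 9.8.1 takes a difference of 0.26 (SD 0.94) for daytime symptoms and −1.34 puffs (SD 3.82) for SABA use from two montelukast studies. Table 9-2 then gives:

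| | Symptoms | SABA |
|---|---|---|
| Power at alpha 0.0245 | 74% | 97% |
| Power at alpha 0.05 | 83% | 98% |

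SAP Table 3-2 repeats these figures. The text concludes that "all secondary endpoints have an adequate conditional power once the primary null hypothesis has been rejected".

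The footnote covers all columns together: 10,000 trials, 250 jump-to-reference imputations, and two common assumptions. "We assumed a treatment discontinuation rate of 15% with half of the patients discontinuing from study treatment completing the trial" (SAP Table 3-2), and "The correlation structure was assumed to be the same as for the primary endpoint" (Protocol Table 9-2).

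The planned analyses have the same form. For symptoms, section 9.5.1.1 says "The mean of change from baseline in the daytime symptom scores over the 12 weeks of treatment will be analyzed"; for SABA, section 9.5.1.2 says "The mean of change from baseline in the total daily use of SABA over the 12 weeks of treatment will be analyzed". Both use an ANCOVA modelled on the primary analysis.

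**The concern.** With sample size, alpha, discontinuation, correlation and imputation held in common, rescaling an outcome does not change its test statistic. The only thing that can separate the two columns is delta/SD. SABA has the larger standardised effect and should have more power, but the printed gap is wider than the inputs allow.

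These are the stated chances of success for two alpha-controlled secondary endpoints. At least one column misstates its endpoint's power, and a reader cannot tell which. Daytime symptoms has the lowest printed power of the three secondaries, so whether its power at the initial alpha is 74% or about 84% matters to anyone judging what the trial can show.

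**Working it through.** **Inputs.** 325 per arm (Protocol section 9.8). Local alpha: section 9.4.2 sets 5% two-sided overall and says "98% of the alpha will be distributed equally amongst the secondary null hypotheses of daytime asthma symptoms and total daily SABA use", so each gets 0.98 × 0.05 / 2 = 0.0245; the lower block of the table uses 0.05. Critical values are 2.249 and 1.960.

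**Undiluted signal.** Noncentrality θ = (delta/SD) × √(325/2), with √162.5 = 12.748.
- Symptoms: 0.26/0.94 = 0.2766; θ = 3.526.
- SABA: 1.34/3.82 = 0.3508; θ = 4.472.
- Ratio: 4.472/3.526 = 1.268.

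**Reproducing the printed figures.** Each column can be reproduced separately, under different dilutions.
- Effect × 0.85 with n × 0.925 keeps 0.85 × √0.925 = 0.818 of θ. Symptoms: 73.7% / 82.2% (printed 74 / 83). SABA: 92.0% / 95.5% (printed 97 / 98).
- Effect × 0.925 with full n. SABA: 97.0% / 98.5% (printed 97 / 98). Symptoms: 84.4% / 90.3% (printed 74 / 83).

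**Share of θ implied by each printed power.** Share = (critical value + z of the power) / θ. The range allows for rounding of the power to a whole percent.

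| Cell | Implied noncentrality | Share | Range |
|---|---|---|---|
| Symptoms 74%, 0.0245 | 2.249 + 0.643 = 2.893 | 0.820 | 0.816–0.825 |
| Symptoms 83%, 0.05 | 1.960 + 0.954 = 2.914 | 0.826 | 0.821–0.832 |
| SABA 97%, 0.0245 | 2.249 + 1.881 = 4.130 | 0.924 | 0.908–0.941 |
| SABA 98%, 0.05 | 1.960 + 2.054 = 4.014 | 0.898 | 0.877–0.924 |

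Taking both rows together, symptoms need 0.821–0.825 and SABA needs 0.908–0.924. The ranges do not overlap. The implied SABA/symptom ratios are 4.130/2.893 = 1.43 and 4.014/2.914 = 1.38, against 1.27 from the inputs.

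**Carrying one column's share to the other.**
- Symptom share applied to SABA: 92.2–92.5% / 95.6–95.8%.
- SABA share applied to symptoms: 83.0–84.3% / 89.3–90.3%.
- Best single share for all four cells, 0.848: symptoms 77.1 / 84.8, SABA 93.9 / 96.7; worst miss 3.1 points.

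**Noise and rounding.** Monte Carlo SE is √(p(1−p)/10,000): 0.44 and 0.38 points for the symptom cells, 0.17 and 0.14 for SABA. Rounding the inputs as favourably as possible (0.255/0.945 and 1.345/3.815, ratio 1.307), with symptom power at its upper rounding limit, brings SABA at 0.0245 only to about 94%.

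**Simulation check.** The correlation value is not published, so jump-to-reference imputation with Rubin's rules was simulated in 16 settings: compound symmetry (0.5, 0.8) or AR(1) (0.7, 0.9), effect lost or kept in retrieved drop-outs, last visit or mean over visits; 800 trials and 30 imputations each. The retained share was the same for both endpoints to within 0.004 in every setting. Settings giving symptoms about 75–76% / 84–85% gave SABA 93.3–93.9% / 96.4–96.8%. Settings giving SABA about 97% gave symptoms 82–84% or more at 0.0245. None matched all four cells.

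**The case against.** **Different endpoints may have been simulated.** This is the strongest reply. Section 9.8.1 places the symptom difference after 12 weeks of treatment and attaches no such phrase to SABA. If 15% stop evenly over time and lose the effect, a Week 12 endpoint keeps 0.85 of it and a 12-week mean keeps about 0.925. Those are the dilutions that reproduce the two columns above, and the first also gives 97.3% for AQLQ+12 (printed 98%), which is a Week 12 endpoint. The symptom column would then understate power for the planned mean, a conservative error. This is plausible but is an inference. The footnote does not state it, and if true, the symptom column does not describe the planned endpoint and still needs correcting.

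**Rubin's SE may be conservative.** Let r be the ratio of the Rubin SE to the true sampling SD, so that power = Φ(kθ − r × critical value), with k the retained share. The 112 and 100 mL rows of Table 9-1 (θ = 3.757 and 3.355) give k = (1.299 − 0.874)/(3.757 − 3.355), about 1.055, and r = (1.055 × 3.757 − 1.299)/1.960, about 1.36. At that r the best common fit is 74.1 / 85.1 and 95.0 / 97.9, a worst miss of 2.1 points; favourable input rounding cuts this to 1.2. Three things count against it. The estimate is imprecise: one Monte Carlo SE in each power moves r over about 1.2–1.5. The symptom rows themselves give r = (0.954 − 0.643)/(2.249 − 1.960), about 1.07, or 0.95–1.20 after rounding; within that range, even with the most favourable inputs, SABA at 0.0245 reaches at most 95.0%. Direct jump-to-reference simulation with about 7.5% missing gave r of roughly 1.0–1.1, where the miss is still about 3 points. What stands is that the size of the gap depends somewhat on r.

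**Conditioning on earlier rejections.** This does not explain the conflict: within each column the two rows differ as the change in alpha alone predicts, once rounding is allowed for.

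**Consequence.** It is fair that no analysis uses Table 9-2, that the primary endpoint sets the sample size, and that calling the power adequate may survive either way.

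**Conclusion.** The concern holds. Under the footnote's single set of assumptions and the planned 12-week-mean endpoints, the two columns are incompatible.

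- At alpha 0.0245, where the conflict is clearest: SABA about 92% against 97% printed (5 points), or symptoms about 84% against 74% printed (10 points).
- At alpha 0.05: SABA about 96% against 98% (2 points), or symptoms about 90% against 83% (7 points).

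These sizes assume a normal approximation with the Rubin SE close to the true sampling SD. A conservative SE narrows the gap but does not close it within the range the symptom rows allow.

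The documents do not identify the wrong column. The SABA share is out of line with AQLQ+12 (5.344/6.374 = 0.838) and FEV1 (0.845–0.867 from Table 9-1), but those are Week 12 endpoints, so that comparison does not settle the matter. The consequence is limited to the reported power of two secondary endpoints.

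**What to change.** Re-run the symptom and SABA columns with one program, for the planned 12-week mean and under the footnote's assumptions, without presupposing which column stands. Restate the powers in Protocol Table 9-2 and SAP Table 3-2. Add a footnote sentence saying which endpoint form each column simulates and whether the SD is per visit or of the 12-week mean; if any assumption differs between endpoints, state it there.

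The cost is a re-run of existing simulation code, new figures in two tables and one sentence. Sample size, alpha allocation and tests do not change.

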10.1 Regulatory and ethical compliance

This clinical study was designed and shall be implemented, executed and reported in accordance with the ICH Harmonized Tripartite Guidelines for Good Clinical Practice, with applicable local regulations (including European Directive 2001/20/EC, United States Code of Federal Regulations (US CFR) 21, and Japanese Ministry of Health, Labor, and Welfare), and with the ethical principles laid down in the Declaration of Helsinki.

10.2 Informed consent procedures

Eligible patients may only be included in the study after providing written (witnessed, where required by law or regulation), IRB/IEC-approved informed consent, or, if applicable after such consent has been provided by a legally acceptable representative(s) of the patient. Informed consent must be obtained before conducting any study-specific procedures (e.g. all of the procedures described in the protocol). The process of obtaining informed consent must be documented in the patient source documents.

For trials using an Electronic Informed Consent system where a date/timestamp is automatically generated, the system-generated date/timestamp is sufficient; additional input of the date at the time of consent is not required by the patient.

Novartis will provide to investigators in a separate document a proposed informed consent form that complies with the ICH GCP guideline and regulatory requirements and is considered appropriate for this study. Any changes to the proposed consent form suggested by the investigator must be agreed to by Novartis before submission to the IRB/IEC, and a copy of the approved version must be provided to the Novartis monitor after IRB/IEC approval.

Women of child bearing potential must be informed that taking the study treatment may involve unknown risks to the fetus if pregnancy were to occur during the study and agree that in order to participate in the study they must adhere to the contraception requirement for the duration of the study. If there is any question that the patient will not reliably comply, they must not be entered in the study.

10.3 Responsibilities of the investigator and IRB/IEC

Before initiating a trial, the investigator/institution must obtain approval/favorable opinion from the Institutional Review Board/Independent Ethics Committee (IRB/IEC) for the trial protocol, written informed consent form, consent form updates, subject recruitment procedures (e.g., advertisements) and any other written information to be provided to patients. Prior to study start, the investigator is required to sign a protocol signature page confirming his/her agreement to conduct the study in accordance with these documents and all of the instructions and procedures found in this protocol and to give access to all relevant data and records to Novartis monitors, auditors, Novartis Quality Assurance representatives, designated agents of Novartis, IRBs/IECs, and regulatory authorities as required. If an inspection of the clinical site is requested by a regulatory authority, the investigator must inform Novartis immediately that this request has been made.

10.4 Publication of study protocol and results

The key design elements of this protocol will be posted in a publicly accessible database such as clinicaltrials.gov. In addition, upon study completion and finalization of the study report the results of this trial will be either submitted for publication and/or posted in a publicly accessible database of clinical trial results.

10.5 Quality Control and Quality Assurance

Novartis maintains a robust Quality Management (QM) system that includes all activities involved in quality assurance and quality control, including the assignment of roles and responsibilities, the reporting of results, and the documentation of actions and escalation of issues identified during the review of quality metrics, incidents, audits and inspections.

Audits of investigator sites, vendors, and Novartis systems are performed by Novartis Pharma Auditing and Compliance Quality Assurance, a group independent from those involved in conducting, monitoring or performing quality control of the clinical trial. The clinical audit process uses a knowledge/risk based approach.

Audits are conducted to assess GCP compliance with global and local regulatory requirements, protocols and internal standard operating procedures (SOPs), and are performed according to written Novartis processes.

11 Protocol adherence

This protocol defines the study objectives, the study procedures and the data to be collected on study participants. Additional assessments required to ensure safety of patients should be administered as deemed necessary on a case by case basis. Under no circumstances including incidental collection is an investigator allowed to collect additional data or conduct any

additional procedures for any purpose involving any investigational drugs under the protocol, other than the purpose of the study. If despite this interdiction, data, information, observation would be incidentally collected, the investigator shall immediately disclose it to Novartis and not use it for any purpose other than the study, except for the appropriate monitoring on study participants.

Investigators ascertain they will apply due diligence to avoid protocol deviations. If an investigator feels a protocol deviation would improve the conduct of the study this must be considered a protocol amendment, and unless such an amendment is agreed upon by Novartis and approved by the IRB/IEC and health authorities, where required, it cannot be implemented.

